Because of the possibility of an initial increase in tumor burden caused by immune cell infiltration in the setting of a T-cell response (termed pseudoprogression) with immunotherapy treatment, radiographic progression defined as unconfirmed progressive disease according to iRECIST ([Seymour 2017](#)) may not be indicative of true PD. Hu5F9-G4 and cetuximab combination treatment may continue past the initial determination of disease progression according to iRECIST as long as the following criteria are met:

- No new symptoms or worsening of previous symptoms
- Tolerance of Hu5F9-G4 and avelumab
- Stable ECOG performance status
- Treatment beyond progression will not delay an imminent intervention to prevent serious complications of disease progression (for example, central nervous system [CNS] metastases)

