#### **10.2.2. Assessment of Target Lesion Response**

When more than 1 measurable lesion is present at baseline all lesions up to a maximum of 5 lesions total (and a maximum of two lesions per organ) representative of all involved organs should be identified as target lesions. Target lesions should be selected on the basis of their size (lesions with the longest diameter), be representative of all involved organs, but in addition should be those that lend themselves to reproducible repeated measurements.

Complete Response (CR): Disappearance of all target lesions. Any pathological lymph nodes (whether target or non-target) must have reduction in short axis to < 10 mm.

Partial Response (PR): At least a 30% decrease in the sum of diameters of target lesions, taking as reference the baseline sum diameters.

Progressive Disease (PD): At least a 20% increase in the sum of diameters of target lesions, taking as reference the smallest sum measured while on study (this includes the baseline sum if that is the smallest on study). In addition to the relative increase of 20%, the sum must also demonstrate an absolute increase of at least 5 mm.

However, because patients treated with immunotherapies may show pseudoprogression, patients with PD may continue investigational treatment through

RECIST Version 1.1-defined radiological progression of disease until disease progression is confirmed  $\geq$  4 weeks later (Nishino 2013; Hodi 2016) provided that all of the following apply: absence of clinical symptoms or signs indicating clinically significant disease progression; no decline in performance status; absence of rapid disease progression, or threat to vital organs or critical anatomical sites (e.g., CNS metastasis, respiratory failure due to tumor compression, or spinal cord compression) requiring urgent alternative medical intervention; and no significant unacceptable or irreversible toxicities related to study treatment. If the confirmation scan demonstrates pseudoprogression and not PD, the patient may continue on treatment until disease progression is confirmed. The appearance of one or more new lesions is also considered progression according to RECIST Version 1.1 guidelines, however patients who meet the above criteria for non-clinically significant disease progression may also continue treatment until disease progression is confirmed (Hodi 2016).

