#### **10.2.3. Assessment of Non-target Lesions**

CR: Disappearance of all non-target lesions and normalization of tumor marker level. All lymph nodes must be non-pathological in size (< 10 mm short axis).

Non-CR/Non-PD: Persistence of one or more non-target lesion(s) and/or maintenance of tumor marker level above the normal limits.

PD: Unequivocal progression of existing non-target lesions. However, because patients treated with immunotherapies may show pseudoprogression, patients with PD may continue investigational treatment through RECIST Version 1.1-defined radiological progression of disease until disease progression is confirmed  $\geq$  4 weeks later (Nishino 2013, Hodi 2016), provided that all of the following apply: absence of clinical symptoms or signs indicating clinically significant disease progression; no decline in performance status; absence of rapid disease progression or threat to vital

organs or critical anatomical sites (e.g. CNS metastasis, respiratory failure due to tumor compression, spinal cord compression) requiring urgent alternative medical intervention; and no significant unacceptable or irreversible toxicities related to study treatment. If the confirmation scan demonstrates pseudoprogression and not PD, patients may continue on treatment until disease progression is confirmed.

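### Protocol 6.1.1 makes treatment past first progression depend on tolerance of avelumab, which is not a study drug, and 10.2.2 and 10.2.3 give a second, unlinked list for the same decision

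*Protocol*

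**What the plan says.** Protocol Section 6.1.1 states that "Hu5F9-G4 and cetuximab combination treatment may continue past the initial determination of disease progression according to iRECIST", subject to four conditions. The first is "No new symptoms or worsening of previous symptoms". The second is "Tolerance of Hu5F9-G4 and avelumab". The third is stable ECOG performance status, and the fourth is that continuing must not hold up an imminent intervention against serious complications of progression.

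Section 10.2.2 also allows treatment to continue, this time past RECIST 1.1 progression and until progression is confirmed at least 4 weeks later. Its conditions are:

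- on symptoms, "absence of clinical symptoms or signs indicating clinically significant disease progression";
- a performance status that has not worsened;
- on the pace and site of disease, "absence of rapid disease progression, or threat to vital organs or critical anatomical sites" that would call for urgent alternative treatment;
- no significant unacceptable or irreversible toxicity from study treatment.

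It then says: "If the confirmation scan demonstrates pseudoprogression and not PD, the patient may continue on treatment until disease progression is confirmed". For new lesions it adds that "patients who meet the above criteria for non-clinically significant disease progression may also continue treatment until disease progression is confirmed". Section 10.2.3 repeats the conditions for non-target lesions and ends in the same way: "If the confirmation scan demonstrates pseudoprogression and not PD, patients may continue on treatment until disease progression is confirmed".

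Section 10.3.1.1 defines confirmed progression under iRECIST (iCPD), with explicit worsening criteria and a scan 4 to 8 weeks after the unconfirmed progression (iUPD). Section 8.1 lists tumor progression, including iRECIST-confirmed progression, among the possible reasons to stop study drugs. Section 3.9 and the synopsis (Duration of Treatment) say that treatment runs until progression, toxicity or refusal, and mention no exception.

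**The concern.** This text decides which patients keep receiving two antibodies after a scan has shown progression, so it is an operative rule. One of its conditions names a drug that nobody in the trial receives and does not name the one that every patient is planned to receive with Hu5F9-G4. An investigator who looks in the response-assessment section finds other conditions and no sign that Section 6.1.1 exists. Two sites could both follow the protocol in good faith and treat similar patients differently. The safety conditions on rapid progression and on irreversible toxicity could be missed by a site that reads only 6.1.1.

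**Working it through.** No arithmetic applies. The check sets the sections side by side.

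**1. The drug.** Section 3.1 and Tables 1 and 2 give the regimen as Hu5F9-G4 and cetuximab. Avelumab appears nowhere else in the supplied text. The sentence that introduces the 6.1.1 list names cetuximab, so the intended drug is evident and the condition is an error in current body text.

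**2. Is it the same decision?** Section 6.1.1 is triggered by unconfirmed progression under iRECIST, and 10.2.2 and 10.2.3 by progression under RECIST 1.1. Section 10.3.1.1 and the notes to Table 14 build iRECIST progression on the RECIST 1.1 definitions. In practice one scan triggers both lists.

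**3. The conditions compared.**

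- *Symptoms.* 6.1.1 rules out any new or worse symptom. 10.2.2 and 10.2.3 rule out only symptoms or signs of clinically significant progression.
- *Performance status.* Stable in one list, no decline in the other: essentially the same.
- *Tolerability.* Hu5F9-G4 and avelumab in 6.1.1. In 10.2.2 and 10.2.3, no significant unacceptable or irreversible toxicity from study treatment, which covers cetuximab.
- *Rapid progression.* Only in 10.2.2 and 10.2.3.
- *Threat to vital organs or critical sites.* Named only in 10.2.2 and 10.2.3. The imminent-intervention condition in 6.1.1 overlaps with it in part.

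Two cases show the difference. A patient with one minor new symptom unrelated to the tumor fails the 6.1.1 list but can pass the 10.2.2 list. A patient with rapid progression, no symptoms and no imminent intervention passes the 6.1.1 list (reading cetuximab for avelumab) but fails the 10.2.2 list.

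**4. Confirmation.** 10.2.2 and 10.2.3 give a minimum of 4 weeks, no upper limit and no measurement criterion, and they do not refer to 10.3.1.1. Section 10.3.1.1 gives 4 to 8 weeks and requires further worsening. If progression is still present without worsening, the assessment remains iUPD. It is therefore unclear whether that rule governs continuation under 10.2.2 and 10.2.3, whose contrast is between pseudoprogression and progression.

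**5. Does another section settle it?** Section 8.1 mentions iRECIST confirmation, but within an open list of possible reasons that begins with tumor progression in general. It does not make iCPD the required standard. Section 3.9 and the synopsis, read alone, allow no treatment past progression.

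**6. Planned analyses.** SAP Section 4 counts the first documented RECIST 1.1 progression, or death, as the PFS event and bases response on RECIST 1.1. SAP Section 7 drops the reporting of iRECIST assessments. Neither the ORR nor the PFS definition depends on which list a site follows.

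**The case against.** The strongest reply is that this is editorial. The lead-in sentence in 6.1.1 makes the intended drug plain. Cetuximab toxicity is handled in Section 6.1.4.2 and Table 3, and Sections 3.9 and 8.1 allow stopping for toxicity. Both lists are permissive: they say that treatment may continue, and a site that applies both breaches neither. The investigator can always stop treatment under 8.1.

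Much of this stands. It shows that the wrong drug name does not leave cetuximab toxicity unmanaged, and that no section forces continuation where another forbids it. It does not make the condition usable as written, and it does not help a site that finds only one of the two lists.

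A reader might also infer that the protocol leaves confirmed progression undefined. It does not: Section 10.3.1.1 defines it, and Tables 14 and 15 apply it. The gap is the missing reference from 10.2.2 and 10.2.3. A reader might go further and infer that a second scan with persistent but not worse progression means stop in 10.2.2 and continue in 10.3.1.1. The stop reading is only an inference, because 10.2.2 has no rule that persistence alone counts as confirmation.

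**Conclusion.** The point holds as a drafting error in an operative treatment rule. One condition in 6.1.1 names the wrong drug. A second list for the same decision differs on symptoms, rapid progression, organ threat and toxicity. Neither the conditions nor the meaning of confirmation are linked across sections.

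The consequence is for consistent and safe treatment conduct. The number of patients affected cannot be estimated from the documents. A reader might infer that efficacy results are at risk, but the planned ORR and PFS definitions are unaffected. Overall survival, exposure and the adverse-event window in SAP Section 6.2, which ends no later than 30 days after the last dose, could in principle follow longer or shorter treatment. The documents give no basis for the direction or size of such an effect.

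The conclusion assumes that cetuximab is the intended drug and that both lists are meant for the same decision; the wording of 6.1.1 and the structure of Section 10 support both assumptions.

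**What to change.** 1. In Section 6.1.1, replace avelumab with cetuximab. Add two conditions to that list: no rapid progression or threat to vital organs or critical anatomical sites, and no unacceptable or irreversible toxicity from study treatment.
2. In Sections 10.2.2 and 10.2.3, refer to 6.1.1 for the conditions and to 10.3.1.1 for confirmation.
3. In Section 3.9 and in the synopsis, after the statement that treatment runs until progression, add that Section 6.1.1 gives the exception.

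Two clinical decisions belong to the sponsor and should be stated openly when the cross-references go in, because the cross-references would otherwise settle them by default. The first is whether the symptom condition means any symptom or only disease-related ones. Read literally, the 6.1.1 wording would stop a patient whose only new symptom is a drug rash, and Section 6.1.4.2.5 reports acneiform rash in 82% of 1373 patients given cetuximab. The second is whether persistent progression without further growth ends treatment.

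The cost is wording in five places (6.1.1, 10.2.2, 10.2.3, 3.9 and the synopsis). No procedure, visit or analysis is added.

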### **6.1.2. Premedication**

Premedication is required before administration of the first cetuximab dose and before the first 2 doses of Hu5F9-G4 (inclusive of the priming dose). At the discretion of the Investigator, administration of premedication may continue for subsequent doses of cetuximab and/or Hu5F9-G4.

#### **Hu5F9-G4**

Premedication with oral acetaminophen 650 to 1000 mg and oral or intravenous diphenhydramine 25 mg, or comparable regimen, is required before administration of the first 2 doses of Hu5F9-G4 (inclusive of the priming dose). Premedication may be given at any time on the day(s) of dosing, up to 15 minutes prior to dosing. Premedication for subsequent Hu5F9-G4 treatments may be continued based upon the treating physician's clinical judgement and the presence/severity of prior

infusion-related reactions. Premedications used to manage infusion-related reactions are described in [Sections 6.1.4.2.2](#) and [6.1.5.2.4](#).

### **Cetuximab**

From 30 to 60 minutes prior to administration of the first dose of cetuximab, patients should be premedicated with an H1 antagonist (e.g., 50 mg of diphenhydramine) intravenously. Continued use of premedications plus the addition of other agents (i.e., glucocorticoids, etc.) should be implemented as required by local standards of practice and at the discretion of the Investigator.

#### **6.1.3. Repriming**

The following list describes the requirements for Hu5F9-G4 repriming.

- Patients who experience an interruption of >2 weeks after receiving only the priming dose (1 mg/kg) must be “reprimed” by receiving the Hu5F9-G4 priming dose of 1 mg/kg IV over 3 hours ( $\pm$ 30 minutes) and 3 subsequent weekly maintenance doses prior to starting the Q2W dosing schedule.
- Patients who experience an interruption of >4 weeks after receiving at least 1 maintenance dose (i.e., 30 mg/kg) must be “reprimed” by receiving the Hu5F9-G4 priming dose of 1 mg/kg IV over 3 hours ( $\pm$ 30 minutes) and 3 weekly maintenance doses prior to starting the Q2W schedule.
- Cetuximab must be administered as regularly scheduled (e.g. Hu5F9-G4 repriming doses may be administered on the same day as cetuximab is given and administration of cetuximab once weekly should be maintained.)
- Premedication is required for the repriming dose and the first weekly maintenance dose ([Section 6.1.2](#)).

On the day that patients receive their repriming dose, a predose ADA sample is to be collected.

For patients who are reprimed, the following assessments are to be performed at the supplemental weekly visits (e.g., Day 8, Day 22):

- Complete blood count (CBC) with differential, platelets, reticulocytes

- Peripheral blood smear
- Serum chemistry
- Haptoglobin, D-dimer, thrombin, fibrinogen
- PT/INR, aPTT
- Vital signs
- Physical examination
- Adverse events
- Concomitant medications

#### **6.1.4. Dose Delays, Dose Modifications, and Safety Management Guidelines**

##### **6.1.4.1. Hu5F9-G4**

Dose modification or dose delay of Hu5F9-G4 may not occur for patients in the initial 28-day DLT assessment period in the Phase 1b part of the study or for patients in the first cycle of the Phase 2 part of the study. After the initial 28-day treatment period for evaluation of DLTs, Hu5F9-G4 may be withheld if treatment-emergent Hu5F9-G4-related AEs occur, which include all AEs that constitute a DLT as defined in [Section 3.2.4](#). If the severity has recovered to Grade 0 to 2 within 4 weeks and in the absence of disease progression, Hu5F9-G4 may be re-introduced at the next lower dose level. Patients who experience a DLT of either hemolytic anemia or Grade  $\geq 4$  non-hematological toxicity will not restart Hu5F9-G4 and will be withdrawn from study drug treatment. Restarting treatment after a delay of more than 4 weeks (such as for an unrelated medical condition with expected recovery) must be approved by the medical monitor.

Patients with an interruption or treatment delay of longer than 2 weeks after receiving only the priming dose (1 mg/kg) or  $>4$  weeks after receiving at least 1 maintenance dose (e.g., 30 mg/kg) must be “reprimed” by receiving the priming dose of 1 mg/kg IV over 3 hours ( $\pm 30$  minutes) and 3 subsequent weekly maintenance doses following the repriming dose prior to resuming the Q2W dosing schedule ([Section 6.1.3](#), Repriming).

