### **Dose-Limiting Toxicity Definition**

Dose escalation decisions will be made by the CTSC based on the first 4 weeks of treatment for each patient, referred to as the “DLT Assessment Period.” The last patient in a cohort must complete the DLT Assessment Period before new patients are escalated to a higher dose level.

Patients assigned to a particular dose cohort in Phase 1b are considered evaluable for assessment of DLT if either of the following criteria are met in the DLT assessment period:

- The patient experienced a DLT at any time after initiation of the first infusion of either Hu5F9-G4 or cetuximab.
- The patient completed at least 4 infusions of Hu5F9-G4 and 2 infusions of cetuximab.

Patients who withdraw before completing the 4-week DLT assessment period for reasons other than a DLT, or who do not fulfill either of the criteria above, will not be evaluable for assessment of DLT for dose review decisions and will be replaced in the cohort.

All toxicities will be graded according to the NCI CTCAE Version 4.03 ([Appendix B](#)), which provides additional guidance for AEs not specifically mentioned in CTCAE. A DLT is defined as any Grade 3 or greater AE that is assessed as related to study treatment that occurs during the 4-week DLT observation period. DLTs apply only to patients in the Phase 1b part of the study.

The following are exceptions to the DLT definition and will NOT be considered a DLT:

- Grade 3 anemia; however, Grade 3 hemolytic anemia that is medically significant, requiring hospitalization or prolongation of existing hospitalization, disabling, or limiting self-care activities of daily life (ADLs) is considered a DLT.
- Grade 3 indirect/unconjugated hyperbilirubinemia that resolves to ≤ Grade 2 with supportive care within 1 week and is not associated with other clinically significant consequences.
- Isolated Grade 3 electrolyte abnormalities that resolve to ≤ Grade 2 with supportive care within 1 week and are not associated with other clinically significant consequences.
- Grade 3 elevation in alanine aminotransferase, aspartate aminotransferase, or alkaline phosphatase that resolves to ≤ Grade 2 with supportive care within 1 week and is not associated with other clinically significant consequences.
- Grade 3 nausea, vomiting, or diarrhea that resolves to ≤ Grade 2 with supportive care within 72 hours
- Grade 3 fatigue that resolves to ≤ Grade 2 within 2 weeks on study.

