### **3.2.4. Definition of Dose-limiting Toxicity**

All toxicities will be graded according to the NCI CTCAE Version 4.03 ([Appendix B](#)). A DLT is defined as any Grade 3 or greater AE that is assessed as related to study treatment that occurs during the 4-week DLT observation period. DLTs apply only to patients in the Phase 1b part of the study.

The following are exceptions to the DLT definition and will NOT be considered a DLT:

- Grade 3 anemia; however, Grade 3 hemolytic anemia that is medically significant, requiring hospitalization or prolongation of existing hospitalization, disabling, or limiting self-care activities of daily life (ADLs) is considered a DLT.
- Grade 3 indirect/unconjugated hyperbilirubinemia that resolves to  $\leq$  Grade 2 with supportive care within 1 week and is not associated with other clinically significant consequences.
- Isolated Grade 3 electrolyte abnormalities that resolve to  $\leq$  Grade 2 with supportive care within 1 week and are not associated with other clinically significant consequences.
- Grade 3 elevation in alanine aminotransferase, aspartate aminotransferase, or alkaline phosphatase that resolves to  $\leq$  Grade 2 with supportive care within 1 week and is not associated with other clinically significant consequences.
- Grade 3 nausea, vomiting, or diarrhea that resolves to  $\leq$  Grade 2 with supportive care within 72 hours
- Grade 3 fatigue that resolves to  $\leq$  Grade 2 within 2 weeks on study.
- Grade 3 Hu5F9-G4 or cetuximab-related infusion reactions in the absence of an optimal pretreatment regimen, which is defined as acetaminophen or a comparable non-steroidal anti-inflammatory agent, plus an antihistamine and corticosteroids.
- Grade 3 tumor lysis syndrome or electrolyte disturbances (hyperkalemia, hypophosphatemia, hyperuricemia) that resolve to  $\leq$  Grade 2 or baseline within 1 week
- Grade 3 hypomagnesemia, that resolves to  $\leq$  Grade 2 within 1 week

- Grade 3 or 4 lymphopenia or leukopenia

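### Section 6.1.4.1 ties its mandatory permanent Hu5F9-G4 stop to a DLT, a term the cited Section 3.2.4 confines to the first 4 weeks of Phase 1b

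*Protocol*

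**What the plan says.** Protocol Section 6.1.4.1 gives the Hu5F9-G4 dose delay and modification rules for both phases. It does four things.

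- It bars delay or modification in the 28-day DLT assessment period of Phase 1b and "for patients in the first cycle of the Phase 2 part of the study".
- After the initial 28 days it allows the drug to be withheld for Hu5F9-G4-related events, "which include all AEs that constitute a DLT as defined in" Section 3.2.4.
- If the event recovers to Grade 0 to 2 within 4 weeks and the disease has not progressed, "Hu5F9-G4 may be re-introduced at the next lower dose level". Medical monitor approval is required only when the delay exceeds 4 weeks.
- It then sets the mandatory stop. The sentence opens "Patients who experience a DLT of either hemolytic anemia or Grade", goes on to non-hematological toxicity of Grade 4 or higher, and says these patients "will not restart Hu5F9-G4 and will be withdrawn from study drug treatment".

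Section 3.2.4 defines a DLT as a treatment-related event of Grade 3 or higher that "occurs during the 4-week DLT observation period. DLTs apply only to patients in the Phase 1b part of the study". The synopsis repeats the phase limit: "DLTs apply only to patients in the Phase 1b part of the study". Ordinary Grade 3 anemia is excepted, but "Grade 3 hemolytic anemia that is medically significant, requiring hospitalization or prolongation of existing hospitalization, disabling" or limiting self-care still counts as a DLT.

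**The concern.** The stop is a patient-safety rule, and the word that triggers it is defined more narrowly than the paragraph that uses it. Section 6.1.4.1 governs Phase 2 and the time after Day 28. Under the definition it cites, no DLT can occur in either.

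At stake is how a serious event is handled after it resolves. Suppose a patient has a Hu5F9-G4-related Grade 4 non-hematological event in Cycle 3 that recovers to Grade 1 in two weeks without progression. A site that applies Section 3.2.4 finds no DLT and may restart at the next lower dose. A site that reads the paragraph by its context must stop for good. Each has text to point to.

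The uncovered periods are not marginal. Phase 1b patients may be escalated to a higher maintenance dose only after at least 8 weeks on study (Section 6.1.4.1.3), so the whole escalated period lies outside the defined window. Phase 2 may also test 45 mg/kg (Table 2) without a further safety run-in (Section 3.1).

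**Working it through.** There is no figure to reproduce. The check is to apply each reading of the trigger to each treatment period, then look for another rule that would require the same stop.

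**Step 1. The two readings.** The definitional reading takes a DLT exactly as Section 3.2.4 has it: within 4 weeks and in Phase 1b only. The event-type reading borrows the grades and exceptions of Section 3.2.4 but not its time and phase limits.

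| Period | Stop required, definitional reading | Stop required, event-type reading | Other rule in Section 6.1.4.1 |
|---|---|---|---|
| Phase 1b, first 28 days | Yes | Yes | No delay or modification |
| Phase 1b, after Day 28 | No | Yes | May hold; may re-introduce one level lower after recovery |
| Phase 2, Cycle 1 | No | Yes | No delay or modification |
| Phase 2, after Cycle 1 | No | Yes | May hold; may re-introduce one level lower after recovery |

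**Step 2. Where the action differs.** In the second and fourth rows the definitional reading permits a restart that the event-type reading forbids. In the third row holds are barred, so hold-and-restart does not arise. There the difference is only whether a stop is compulsory.

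**Step 3. The safety run-in.** Section 3.3 applies a DLT period and a DLT rate to the first 9 KRAS wild-type patients in Phase 2, and SAP Section 2 extends DLT evaluability to them. If that use overrides Section 3.2.4, the stop reaches those 9 patients in their first 4 weeks. It still does not reach them later, or any other Phase 2 patient.

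**Step 4. Other rules.**

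- Section 6.1.5.2.4 requires permanent discontinuation, but for infusion reactions only.
- The permanent stops in Section 6.1.4.2 concern cetuximab toxicities.
- Section 8.1 lists unacceptable toxicity and investigator decision among possible reasons for withdrawal. Section 3.9 lets treatment run until unacceptable toxicity. Both rest on judgement.
- Section 9.4 sends serious events to the sponsor within 24 hours, with related fatal or life-threatening events going to the Medical Monitor. Section 3.5 has the steering committee meet on emergent critical safety data. These are oversight, not a patient-level stop.

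No other section requires a permanent stop for hemolytic anemia or for Grade 4 or higher non-hematological toxicity in general.

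**Step 5. Does the proposed trigger alter the existing Phase 1b rule?** Every exception in Section 3.2.4 concerns Grade 3 events, apart from Grade 3 or 4 lymphopenia or leukopenia, which are hematological. So any treatment-related Grade 4 or higher non-hematological event in the window is already a DLT. Grade 4 hemolytic anemia is one too, because only Grade 3 anemia is excepted. Naming the events directly leaves the rule for the first 4 weeks of Phase 1b unchanged.

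**The case against.** The strongest reply is that the paragraph explains itself. It speaks of events after Day 28 that amount to DLTs, which is empty if DLTs end at Day 28. The stop sentence forbids a restart, which presupposes a hold, and holds are barred in the first 28 days. On the definitional reading it would have almost nothing to act on. The limits in Section 3.2.4 sit among the dose-escalation rules, and the protocol itself relaxes them for the run-in. Early single-agent experience in Section 1.2.4.1 (17 patients) reports very few drug-related toxicities after the first cycle.

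Most of this stands: the event-type reading is probably what was meant. It does not settle the matter, because it asks a site to set aside an express sentence in the section the paragraph cites. The early experience also offers no comfort for Phase 2 Cycle 1, which is when most drug-related findings occur.

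A reader might infer more than the documents support:

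- *That Phase 2 patients cannot be taken off the drug, or must be re-challenged.* They can be stopped at any time, and re-introduction is optional and conditional.
- *That the restart-or-stop conflict runs through all of Phase 2.* It cannot arise in Cycle 1.
- *That the absence of a DLT assessment from the Phase 2 schedule proves the narrow reading.* The schedules list assessments, not stopping rules, and adverse events are collected throughout Phase 2.
- *That the number of patients or days outside the DLT window measures the risk.* Such counts only restate the definitional reading.

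**Conclusion.** The point holds as a conflict between a mandatory safety rule and the definition it cites. It should be corrected, though it does not show that patients are unprotected.

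The conclusion rests on the cross-reference to Section 3.2.4 being taken at its word. On that basis the permanent stop does not apply in Phase 1b after Day 28 or in Phase 2, except arguably to the 9 run-in patients in their first 4 weeks.

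Outside Phase 2 Cycle 1, sites would act differently only if four things coincide: a Hu5F9-G4-related event of the named kind, recovery to Grade 0 to 2 within 4 weeks, no progression, and a decision to restart. The documents give no frequency for this, so none is estimated. Reporting and committee review would probably bring a divergence to light, but they do not say which rule governs.

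**What to change.** In Section 6.1.4.1, replace the DLT-based trigger with the events themselves:

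> *a treatment-related hemolytic anemia that meets the Section 3.2.4 severity criteria (including Grade 4), or a treatment-related Grade ≥4 non-hematological toxicity, at any time in Phase 1b or Phase 2 (including Phase 2 Cycle 1), regardless of the time and phase limits in Section 3.2.4*

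The consequence stays as written. If the sponsor did intend the stop only for the first 4 weeks of Phase 1b, the section should say so and give the rule for every other period.

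The cost is one phrase at the next amendment and a note to sites. No data or patients are added. Section 3.2.4 is untouched, so dose escalation, the run-in DLT rate and the SAP's DLT Evaluable Analysis Set are unaffected. The real downside is clinical: a few patients with a reversible Grade 4 event who might have tolerated a lower dose would be permanently stopped.
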